## 5 Introduction

Chronic obstructive pulmonary disease (COPD) is the fifth biggest cause of death in the United Kingdom (UK) and second most common cause of hospital admissions. The UK population prevalence is 1.5% (5.1% in the United States of America, USA). As per the UK Office for National Statistics, COPD was the underlying cause of death in 30,858 cases in England and Wales in 2015. The direct cost of treating COPD is £1.9 billion annually. Innovative improvements in healthcare delivery, including strategies to prevent hospital readmission are essential.

In the USA, across a selection of 15 states in 2008, there were 190,700 index admissions with a principal diagnosis of COPD. The 30-day readmission rate for an acute exacerbation of COPD (AECOPD) was 7.1% and the rate of 30-day readmissions for other primary diagnoses but with COPD as an additional diagnosis was 17.3 percent. Indeed, these data indicate that COPD accounts indirectly and directly for one out of five readmissions to hospital within 30 days. Healthcare costs were consistently higher for readmissions than for initial stays. Cost for the 30-day readmission, with COPD as principal diagnosis, was 18% higher than for the index stay. Costs were more than 50% greater for the readmission with COPD as any diagnosis or for all-cause readmissions. Currently in the UK, several European countries and the USA, healthcare providers and institutions face financial penalties for patients who are readmitted within 30 days. The additional healthcare costs could be reduced by innovative approaches directed to reduce hospital readmission.

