### **Secondary objectives:**

#### **Clinical:**

- To validate NRD as an advanced physiological biomarker of clinical respiratory deterioration and re-exacerbation of COPD.
- To analyse NRD trajectory as it relates to standardly subjective measurements of respiratory symptoms e.g. COPD Assessment Test or the EXACT-PRO questionnaire.
- To determine positive and negative predictive value of NRD to predict re-exacerbation of COPD.
- To investigate composite clinical features to detect re-exacerbation of COPD.
- To assess correlation of change in NRD, physical activity and symptom resolution.

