#### **Technical:**

- To use the data collected during the study to tune, refine, optimise the automated NRD calculation algorithm

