AECOPD is a clinical diagnosis made when a patient with COPD experiences a sustained (e.g. 24–48 h) increase in cough, sputum production, and/or dyspnoea. It commonly occurs in the cohort of patients under investigation in this study, who are at high risk of developing an AECOPD and indeed 20% will be readmitted to hospital within 28 of being discharged (when the primary reason for admission was AECOPD). The Chief Investigator and Principal Investigator therefore deem AECOPD to be an expected AE and SAE and AECOPD will not be reported to the sponsor. In the event of a participant developing an AECOPD, this will be documented in the participant's medical notes and case record file.

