## **14 Statistical considerations**

### **14.1 Sample size calculation (some pilot/feasibility studies may not require a formal sample size calculation)**

A sample size of 30 has been set. This study is a pilot feasibility study with no prior data to power the sample size. As such, the sample size was not determined based on power analysis but will provide sufficient data to inform a larger future study. Data collected during this study will be used for sample size calculation for validation of future work. Recruitment will continue until 30 patients have completed the study.

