### **14.2 Statistical analysis**

For all analyses,  $p<0.05$  will be deemed statistically significant. Comparison of data with one or more factors will be analysed using independent or paired t-test and ANOVA with repeated measures (if needed) for normally distributed data, and non-parametric tests in cases of non-normally distributed data, whenever applicable. Measures of association between the defined indices of NRD, the monitored endpoints and routinely used metrics will be investigated (e.g. using regression analysis). At last, univariate and multi-variate logistic regression may be employed to evaluate the predictive value of a number of investigated features (using the Receiver Operating Characteristic Methodology).

Interim analysis will be performed after 5 patients have been readmitted.

[name] (King's College London) will be involved in statistical analysis for the study. The Lane Fox Research Unit has an existing contract with [name] for *ad hoc* statistical support.

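### Section 14.2 allows multivariable logistic/ROC modelling of an open list of features in 30 patients, so an in-sample AUC can look useful when there is no signal

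*Protocol*

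**What the plan says.** - **Method.** Section 14.2: "univariate and multi-variate logistic regression may be employed to evaluate the predictive value of a number of investigated features", using ROC methodology. The number of features is left open.
- **Purpose.** A clinical secondary objective in section 6 is "To investigate composite clinical features to detect re-exacerbation of COPD", so joint modelling serves a stated aim. Positive and negative predictive value for re-exacerbation is another.
- **Sample.** Section 14.1: "A sample size of 30 has been set", "the sample size was not determined based on power analysis", and "Recruitment will continue until 30 patients have completed the study".
- **Event rate.** The only rate given for this cohort is in section 11, under the SAE definition: "indeed 20% will be readmitted to hospital within 28 of being discharged" (the unit, presumably days, is missing). The Introduction also cites a US figure: "The 30-day readmission rate for an acute exacerbation of COPD (AECOPD) was 7.1" per cent.
- **Outcome.** The objectives concern re-exacerbation. Section 5 defines it as COPD admission, physician-assessed exacerbation or self-treated exacerbation, and gives no rate for it.
- **Same data, second use.** A technical objective in section 6 is "To use the data collected during the study to tune, refine, optimise the automated NRD calculation algorithm".
- **Use of the result.** Section 5 says that if home measurement proves practical and NRD succeeds in detecting and predicting exacerbations, a study validating patient self-use will follow.

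**The concern.** A logistic model fitted and scored by ROC in the same patients always looks better than it would in new patients. The gap grows as events become fewer and predictors more numerous. Here events are few and the predictor list is open. Sections 5 and 9.3 offer three NRD indices, EXACT-PRO, CAT, FEV1, FVC, IC and about ten accelerometer measures, so a model with 3 to 5 features would not be unusual.

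At stake is the reading of success in section 5. If an apparent AUC of 0.7 to 0.8 is taken as showing that NRD predicts exacerbation, the validation study could be launched, or sized, on overfitting.

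**Working it through.** **Inputs.** N = 30 completers (section 14.1). Readmission rate 20% (section 11). The number of predictors k and the re-exacerbation count are not in the protocol. They are assumptions, varied below.

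**The plan's own figure.** The 30 cannot be reproduced, because no effect size, power or precision target is given. The protocol states no AUC.

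**Expected events.** 30 × 0.20 = 6.0 readmissions. The binomial 95% range is 2 to 11. At the US rate of 7.1%, 30 × 0.071 = 2.1. Re-exacerbation includes events treated outside hospital, so its count is probably above 6. I take 6 to 15 as an assumed range.

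**Events per predictor.** At 6 events: 6/3 = 2.0 and 6/5 = 1.2. At 15 events: 15/5 = 3.0.

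**Apparent AUC from noise.** Each dataset has 30 patients, a fixed event count and k independent standard-normal predictors unrelated to outcome (true AUC 0.50). A logistic fit is scored in the same patients, with 1,500 datasets per cell. Cells show mean AUC, with the share of datasets at 0.80 or above in brackets.

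| Events | k = 1 | k = 2 | k = 3 | k = 5 | k = 8 |
|---|---|---|---|---|---|
| 6 | 0.602 (1%) | 0.659 (6%) | 0.713 (16%) | 0.775 (38%) | 0.871 (78%) |
| 10 | 0.591 (1%) | 0.639 (3%) | 0.679 (8%) | 0.740 (23%) | 0.814 (58%) |
| 12 | 0.586 (1%) | 0.633 (2%) | 0.669 (5%) | 0.734 (20%) | 0.809 (57%) |
| 15 | 0.583 (1%) | 0.633 (1%) | 0.666 (5%) | 0.725 (17%) | 0.802 (52%) |

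At 6 events an apparent AUC of 0.70 or more occurs in 14%, 32%, 56% and 80% of noise datasets for k = 1, 2, 3 and 5.

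**Cross-check for k = 1.** With one predictor the only thing fitted that affects the AUC is its direction, so the mean should be near 0.5 + SE × √(2/π). The Hanley–McNeil SE at AUC 0.5 with 6 events and 24 non-events is 0.134. This gives 0.5 + 0.134 × 0.798 = 0.607, against 0.602 simulated.

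**One-at-a-time screening.** Reporting the best of 5 or 10 noise features gives a mean AUC of 0.71 or 0.75 at 6 events, and 0.67 or 0.70 at 12. Univariate analysis is therefore not immune if the best feature is picked afterwards.

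**Precision.** SE² = [A(1−A) + (n₁−1)(q₁−A²) + (n₀−1)(q₂−A²)]/(n₁n₀), with q₁ = A/(2−A) and q₂ = 2A²/(1+A). For A = 0.7, q₁ = 0.5385 and q₂ = 0.5765.
- 6 events: SE² = (0.21 + 5 × 0.0485 + 23 × 0.0865)/144, so SE = 0.130 and the 95% half-width is 1.96 × 0.130 = 0.26.
- 12 events: SE = 0.101 and the half-width is 0.20.

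**Effect of the remedy.** Bootstrap optimism correction brings the noise AUC for one or two predictors back to about 0.55 or less.

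**The case against.** Several counter-arguments have force.

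- **The analysis is optional.** Section 14.2 only permits it, names univariate regression first and fixes no number of joint predictors. With one or two predictors the noise AUC at 6 events is 0.60 to 0.66, which is biased but not high. A reader might infer that the plan will yield an inflated AUC. The text supports only that it can.
- **Six is the readmission count.** The models mainly target re-exacerbation. At 12 to 15 events the inflation is smaller, though 3 to 5 noise predictors still reach 0.67 to 0.73.
- **A SAP may exist.** Shrinkage, internal validation and the predictor list are commonly placed there, so their absence from the protocol is not the finding. The finding is the pairing of open-ended joint ROC modelling in 30 patients with a next step that depends on successful prediction.
- **Algorithm tuning.** It is tempting to say that tuning on the same data adds further optimism. Section 9.3 describes the algorithm as signal processing, and nothing says it is tuned against exacerbations. Tuning blind to outcome need not inflate the AUC, so this point is conditional.
- **It is a pilot.** The primary end-point is change in NRD, not an AUC. Section 5 sets no AUC threshold, and the follow-on study would collect new data that could expose an optimistic result. That limits the harm, but not the cost of starting or sizing that study on a biased figure.

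**Conclusion.** The concern holds in limited form. As section 14.2 stands, an in-sample AUC from a joint model in 30 patients can overstate predictive value. With no signal at all, the mean is about 0.71 to 0.78 for 3 to 5 predictors at 6 events, and about 0.67 to 0.73 at 12 to 15 events.

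This rests on independent normal predictors, one record per patient, and assumed values for the event count (6 to 15) and the number of predictors. Correlated predictors would reduce the inflation somewhat. Data-driven selection or cut-offs would increase it.

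The documents do not support saying that overstatement is certain, that a correction has been wrongly omitted, or that composites should carry no AUC, since assessing them is a stated objective. Nor does a cap on predictors make the AUC decisive, because an interval of about ±0.20 to ±0.26 remains.

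**What to change.** In section 14.2:

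1. Make the main predictive model a single pre-specified NRD index, with its expected direction stated.
2. Allow at most one added feature, fitted with Firth or ridge penalisation.
3. Report a bootstrap optimism-corrected AUC with its 95% CI beside the apparent AUC.
4. Label any wider composite model exploratory. Correct its AUC for optimism in the same way, and do not use it to judge success as section 5 describes it.
5. If the NRD algorithm is tuned on study data, do so without access to exacerbation outcomes, or repeat the tuning inside the resampling.

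This needs wording and some analysis time, but no extra patients or visits. The downside is lower and wider performance figures, and fewer features assessed formally.

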#### **Feasibility:**

- To investigate quality of parasternal EMG measurements performed in the home environment

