**Screening and eligibility assessment**

Patients will be identified by the clinical team and enrolled in the study within 16 hours of hospital admission to St Thomas' Hospital as study participants. All efforts will be made to reduce disruption of care and respect patient privacy. Interruption of patient care will be minimized by making sure that study staff only approach potential participants after their initial triage and decision to admit. Study related procedures will commence only after the informed consent form is signed by the subject. The study will be explained to the potential participant and sufficient time provided to the subject to ask questions regarding the study (minimum 1 hour). Before signing the consent form, the participant will also be shown the Patient Information Sheet that details the steps of the study procedure to them.

If the participants develop any of the exclusion criteria listed below between enrolment and as the study proceeds, they will be asked to discontinue from the study.

Approximately 300 patients are admitted with COPD per year. Based on previous research conducted by the group in this area there would be expected to be 4-5 eligible patients per week with 2 patients recruited each week.

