#### **9.6 End of Study Definition**

The trial will cease when the final patient has completed 30 days of home monitoring or has an exacerbation requiring hospital re-admission or 12 months from trial initiation, whichever is sooner.

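### Does the interim analysis after 5 readmissions, when about 6 are expected in 30 patients, need a different trigger or significance level?

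*Protocol*

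**What the plan says.** - Section 14.2 plans one unscheduled look: "Interim analysis will be performed after 5 patients have been readmitted". It gives no purpose, hypothesis, stopping rule or separate significance level, and does not say which readmissions count.
- The same section opens by saying that p<0.05 "will be deemed statistically significant" for all analyses.
- Section 14.1 sets the sample at 30 without a power calculation and adds: "Recruitment will continue until 30 patients have completed the study".
- Section 11 says of this cohort that "20% will be readmitted to hospital within 28 of being discharged". The unit is missing, evidently days.
- Section 8 (screening and eligibility) expects "4-5 eligible patients per week with 2 patients recruited each week".
- Section 9.6 ends the trial when the last patient has "completed 30 days of home monitoring or has an exacerbation requiring hospital re-admission", or at 12 months. This leaves open whether a readmitted patient counts as a completer.
- The Introduction gives US figures. "The 30-day readmission rate for an acute exacerbation of COPD (AECOPD) was 7.1"%, with a further 17.3% for readmissions under another primary diagnosis with COPD as an additional one. It sums these up as about one readmission in five.
- Section 7.1 lists all-cause readmission within 30 days as a secondary end-point. The primary end-point is the change in NRD before an exacerbation.

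**The concern.** The trigger sits close to the total number of readmissions that the protocol leads one to expect. A planned look may then never take place, or may come when most patients are already enrolled and there is little left to steer. The blanket p<0.05 also appears to cover the interim. If the same NRD hypothesis were tested at both looks, each at 0.05, and either could support a claim, the false-positive rate would exceed 5%. At stake would be an empty commitment in the plan and a modest loss of error control.

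**Working it through.** The protocol gives no figure of its own for the interim, so there is none to reproduce. The inputs are 30 patients (14.1), 5 readmissions (14.2), a 20% rate (section 11), 7.1% and 17.3% (Introduction) and 2 recruits a week (section 8).

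**1. Does the look occur?** Expected readmissions are 30 × 0.20 = 6.0. The chance that the look never occurs is P(X ≤ 4) for X ~ Binomial(n, 0.20).

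| Reading of enrolment | Never occurs |
|---|---|
| exactly 30 enrolled | 0.26 |
| readmitted patients replaced until 30 complete (4 or fewer readmissions among 34) | 0.16 |
| 37 or 38 enrolled | 0.11 or 0.10 |
| recruitment open until the 30th non-readmitted patient finishes day 30 (simulated, median 47 enrolled) | 0.05 |

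**2. How far does the rate matter?** With 30 enrolled:

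| Rate | Expected | Look occurs |
|---|---|---|
| 7.1% (US, readmission for AECOPD) | 2.1 | 0.06 |
| 17.3% (US, other primary diagnosis) | 5.2 | 0.61 |
| 20% (this cohort) | 6.0 | 0.74 |
| 24.4% (7.1% + 17.3%, assuming they add) | 7.3 | 0.89 |

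The 7.1% row applies only if the trigger counts readmissions for AECOPD alone. The readmission end-point in section 7.1 is all-cause, and the Introduction's one in five agrees with the 20%.

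**3. When does it come?** This was simulated with one patient enrolled every 3.5 days. The length of stay (2, 5 or 7 days) and the spread of readmissions over 28 days (even or front-loaded) are assumptions. With 30 enrolled, a median of 25 are already in when the fifth readmission occurs (23 to 26 across the assumptions). In the base case (5-day stay, even spread) the trigger falls before the last enrolment in 54% of runs. With 37 or 38 enrolled the median is 27. The look is therefore late in recruitment.

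**4. Is it nearly the final analysis?** The ratio 5/6 compares the trigger with the unconditional mean. Given that the look occurs, the total is at least 5, and its mean at 20% is 6.9 with 30 enrolled (5/6.9 = 72%), 7.9 with 37 and 8.1 with 38 (63% and 62%). With 30 enrolled, the chance of 7 or more readmissions, given at least 5, is 0.53. The primary end-point also draws on exacerbations managed without admission, so the share of readmissions is not the share of primary information.

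**5. What would two tests at 0.05 cost?** Take two looks at one hypothesis, information fraction 5/6 and correlation √(5/6) = 0.913. Then 1 − P(|Z₁| < 1.96 and |Z₂| < 1.96) = 0.069. A simulated paired t-test on 5 and then 6 events gives 0.072. Across information fractions of 0.5 to 0.9 the range is 0.083 to 0.065. Each figure assumes that either look could support a claim. If only the final test can, and the interim cannot stop or alter the study, the final error stays at 0.05.

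**The case for a change.** The strongest argument for a change is that the protocol commits itself to the look. On its own rate and sample size, with exactly 30 enrolled, that commitment fails about one time in four. A one-sentence edit could call the look descriptive, tie it to a fixed number of discharged patients (say 15 of 30), and reserve p<0.05 for the final analysis. It could then serve the feasibility objective: "To investigate quality of parasternal EMG measurements performed in the home environment". That would cost no extra patients or visits.

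The arithmetic in this argument stands: the trigger is close to the expected total and the look tends to come late. The inference does not. Nothing in the protocol depends on the look, so its absence changes no decision and no result. A look after 15 discharges would expect only 15 × 0.20 = 3 readmissions even with full follow-up, and fewer than 5 with probability 0.84. It would give up the early view of NRD in readmitted patients for a check of data quality. Since the protocol states no purpose for its interim, one cannot show that the substitute serves it better. Calling the look descriptive would write down a purpose of the kind commonly settled in the statistical analysis plan, which is not at hand.

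**Conclusion.** No change is needed. At the protocol's 20%, the look has a 0.26 chance of never occurring with exactly 30 enrolled, and 0.05 to 0.16 if enrolment exceeds 30 to reach 30 completers. It usually falls late in recruitment. These are features of an event-driven look in a small pilot, not a contradiction. The 7% error rate belongs to a procedure that the protocol does not describe: with no stopping rule, sample-size rule or claim attached to the interim, the final test keeps its 5% level. Analysts would sensibly treat the look as descriptive and omit it if the fifth readmission does not come.

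This conclusion rests on the protocol as written. It would change if the unseen statistical analysis plan allowed the interim to stop the study or to support a claim at p<0.05.

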## **15 Ethical considerations**

The study will be performed in line with the declaration of Helsinki and local procedures including approval by the research ethics committee.

## 16 Financing and Insurance

This study is funded by Philips and its Affiliates who supply the NRD measurement equipment (laptop with bespoke NRD analysis software) and physical activity monitors (Philips Actiwatch Spectrum). [name] [name] has allocated funding from the NIHR Biomedical Research Centre at Guy's and St Thomas' NHS Foundation Trust to work on this study.

## 17 Reporting and dissemination

The results of the study will be analysed with the aim to publish at an international respiratory conference and as a peer reviewed journal article in a high ranking respiratory journal. A lay summary of the trial outcomes will be provided by the trial group to the participants and to the Lane Fox Respiratory Unit Patient Association. The study results in lay form will also be uploaded to a trial registry and the research group website to provide visible access to patients and relevant members of the medical profession. The results will also be presented at local clinical and research meetings. The researchers will, where appropriate use social media to increase the visibility of the findings. We will seek patients' permission for unidentifiable de-identified information (without patients' name and personal details) to be transferred to Philips and its Affiliates for internal research and development purposes only following completion of the study.

**Appendix****EXACT-PRO****COPD Assessment Tool**

CAT.pdf

**Extended MRC Dyspnoea score**

1	Breathlessness only with strenuous exercise
2	Breathless when hurrying on the level or walking up a slight hill
3	Walks slower than contemporaries, or stops after walking on the level at own pace
4	Stops for breath after walking 100 m, or for a few minutes, on the level
5	Too breathless to leave the house unassisted
5a	5 but independent in washing and/or dressing
5b	5 and dependent in washing and dressing
